Randomization will be stratified based on diagnosis (candidemia only; invasive candidiasis) and by Acute Physiology and Chronic Health Evaluation (APACHE II) score/absolute neutrophil count (ANC) (APACHE II score ≥ 20 OR ANC < 500 cells/ μ L; APACHE II score < 20 AND ANC ≥ 500 cells/ μ L) at Screening.

Analysis Populations

The analysis populations are defined for this study as follows:

- The intent-to-treat (ITT) population will include all randomized subjects
- The Safety population will include all subjects who received any amount of study drug
- The mITT population will include all subjects who had documented *Candida* infection based on Central Laboratory evaluation of a culture from blood or another normally sterile site obtained ≤ 4 days (96 hours) before randomization and received ≥ 1 dose of study drug
- The clinically evaluable (CE) population will include all subjects in the mITT population who also met inclusion criterion #4, did not meet exclusion criteria #1, #2, or #5, had an assessment of both mycological and clinical response at Day 14 in the window of Day 14 (± 1 day) (subjects with invasive candidiasis documented by radiologic/imaging evidence also must have an assessment of radiologic response), and did not have any other factor that could confound the assessment of the global response at Day 14
- Pharmacokinetic Analysis Population will include all Rezafungin for Injection subjects with at least 1 plasma sample obtained for PK analysis

Statistical Methodology

The primary efficacy outcome for the FDA is ACM at Day 30 (-2 days). The number and percentage of subjects in each treatment group who are alive and deceased at Day 30 will be determined in the mITT population. A two-sided 95% confidence interval (CI) for the observed difference in the ACM rate (Rezafungin for Injection group minus caspofungin group) will be calculated using the unadjusted method of Miettinen and Nurminen. If the upper bound of the 95% CI is lower than 20%, NI of Rezafungin for Injection will be concluded.

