13.4.1 Primary Efficacy Analyses for the FDA

The primary efficacy outcome for the FDA is ACM at Day 30 (-2 days). The addendum to ICH E9 introduces the concept of an estimand which translates the trial objective into a precise definition of the treatment effect that is to be estimated. The description of the estimand includes four attributes: the population, the variable (or endpoint) to be obtained for each patient, the specification of how to account for intercurrent events (ICE), and the population-level summary for the variable. The estimand attributes for ACM at Day 30 are provided in detail in the SAP.

The number and percentage of subjects in each treatment group who are alive and deceased (or with missing data) at Day 30 will be determined in the mITT population.

The null and alternative hypotheses are the following:

$$H_0: P_1 - P_2 \geq \Delta$$

$$H_1: P_1 - P_2 < \Delta$$

Where:

P_1 = the primary efficacy outcome in the Rezafungin for Injection group,

P_2 = the primary efficacy outcome in the caspofungin group,

Δ = the non-inferiority (NI) margin of 20%.

The NI hypothesis test is a 1-sided hypothesis test performed at the 2.5% level of significance. This is based on the upper limit of the 2-sided 95% CI for the observed difference in the rate of ACM at Day 30 (Rezafungin for Injection group minus the caspofungin group). The primary analysis is based on a CI computed using the unadjusted methodology of Miettinen and Nurminen. If the upper limit of the 95% CI for the difference in rates of ACM at Day 30 in

the mITT population is <20%, the null hypothesis will be rejected and the NI of Rezafungin for Injection to caspofungin will be concluded.

An adjusted 95% CI (adjusted for the randomization stratification factors) will also be computed using the methodology of Miettinen and Nurminen. Cochran-Mantel-Haenszel weights will be used for the stratum weights in the calculation of the CI.

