13.4.1.1 Additional Analyses of the FDA Primary Efficacy Outcome

To control the overall alpha level, superiority of rezafungin for ACM at Day 30 will be tested in the following order:

- If NI is declared for ACM at Day 30 in the mITT population and the rate of ACM at Day 30 in the rezafungin treatment group is lower than the caspofungin treatment group, the difference between the treatment groups will be tested for superiority. If the upper bound of the 95% CI is less than 0, superiority of rezafungin will be concluded.
- For the subgroup of subjects with invasive candidiasis, a two-sided 95% CI for the observed difference in the rate of ACM at Day 30 will be calculated using the unadjusted methodology of Miettinen and Nurminen. If superiority is declared in the mITT population for ACM at Day 30 and the rate of ACM at Day 30 in the rezafungin treatment group is lower than the caspofungin group for invasive candidiasis subjects, superiority of rezafungin will be tested. If the upper bound of the 95% CI is less than 0, superiority of rezafungin will be concluded.

All-cause mortality at Day 30 will be assessed separately across the randomization stratification factors of diagnosis (candidemia only; invasive candidiasis) and APACHE II score/ANC (APACHE II score ≥ 20 OR ANC < 500 cells/ μ L; APACHE II score < 20 AND ANC ≥ 500 cells/ μ L). For each subgroup, the number and percentage of subjects alive and deceased at Day 30 will be determined by treatment group in the mITT population. A 2-sided 95% CI for the observed difference in rates of ACM at Day 30 will be calculated in the mITT population using the unadjusted methodology of Miettinen and Nurminen. Other subgroup analyses, including analyses by the pre-, peri-, and post-COVID-19 period will be conducted for descriptive purposes. Depending on the number of subjects in the study diagnosed with COVID-19, ACM at Day 30 may be analyzed in patients with and without COVID-19.

A sensitivity analysis of the primary outcome using multiple imputation methods for missing data, as detailed in the SAP, for subjects whose survival status is not known at Day 30 will be conducted.

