13.4.2 Primary Efficacy Analyses for the EMA

The primary efficacy outcome for the EMA is global cure at Day 14 (± 1 day) based on the DRCs determination. Global response is a composite estimand and ICEs are incorporated into the

variable/endpoint. The estimand attributes for global response are provided in more detail in the SAP.

The number and percentage of subjects in each treatment group who have a global response of cure, failure and indeterminate at Day 14 (± 1 day) will be determined in the mITT population.

The null and alternative hypotheses are the following:

$$H_0: P_1 - P_2 \leq -\Delta$$

$$H_1: P_1 - P_2 > -\Delta$$

Where:

P_1 = the primary efficacy outcome in the Rezafungin for Injection group,

P_2 = the primary efficacy outcome in the caspofungin group,

Δ = the NI margin of 20%.

The NI hypothesis test is a 1-sided hypothesis test performed at the 2.5% level of significance. This is based on the lower limit of the adjusted (for the randomization stratification factors) 2-sided 95% CI for the observed difference in global success rate (Rezafungin for Injection group minus the caspofungin group). The primary analysis is based on a CI computed using the method with stratification by Miettinen and Nurminen. Cochran-Mantel-Haenszel weights will be used for the stratum weights in the calculation of the CI. If the lower limit of the 95% CI for the difference in global success rates in the mITT population is $> -20\%$, the null hypothesis will be rejected and the NI of Rezafungin for Injection to caspofungin will be concluded.

To control the overall alpha level, superiority of rezafungin for global response will be tested in the following order:

- If NI is declared and the percentage of subjects that have a global response of cure at Day 14 (± 1 day) as confirmed by the DRC in the rezafungin treatment group is higher than the caspofungin treatment group, the difference between the treatment groups will be tested for superiority. If the lower bound of the 95% CI is greater than 0, superiority of rezafungin will be concluded.

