1.2.1. Randomization and Blinding

After informed consent has been obtained, subjects will be screened for study eligibility before randomization.

Subjects will be assigned a subject number and randomized (1:1) to receive either IV Rezafungin for Injection or IV caspofungin. The randomization will be stratified based on the following factors at Screening:

- diagnosis (candidemia only; invasive candidiasis) and
- Acute Physiology and Chronic Health Evaluation (APACHE II) score/ absolute neutrophil count (ANC) (APACHE II score ≥ 20 OR ANC < 500 cells/ μL ; APACHE II score < 20 AND ANC ≥ 500 cells/ μL) at Screening

If a subject has a positive result for both blood culture/rapid in vitro diagnostic (IVD) and culture specimen obtained from a normally sterile site, the subject will be randomized to the invasive candidiasis stratum.

The study site's pharmacist (or pharmacist designee) will obtain the study drug assignment via an Interactive Response Technology (IRT). Randomized subjects will be assigned the study drug corresponding to the next available randomization number in the respective stratum from the computer-generated randomization schedule. A subject is considered randomized when the randomization transaction is recorded in the IRT.

All study personnel, including the Sponsor, Principal Investigator (PI), and site personnel involved in study conduct, and subjects will remain blinded to study medication assignment until the study is completed and the database is locked, except for the pharmacy monitor, unblinded program manager, clinical supplies, document manager, and quality (additional details are presented in the Sponsor Blinding Plan). The Pharmacy Monitor will monitor drug preparation and drug accountability during the study and cases in which unblinding is required due to a safety or tolerability issue. The Data and Safety Monitoring Board (DSMB) will be unblinded to safety data for safety reviews as defined in the DSMB Charter.

1.2.2. **Unblinding**

This study is a double-blind design. The PI, study personnel, and subjects will not make any effort to determine which study drug treatment is being received. Unblinded pharmacy personnel and an independent unblinded statistician for preparation of the DSMB report will be utilized in this study.

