2.8. Subgroup analyses

Subgroup analyses will be conducted for the FDA and EMA primary efficacy endpoints. The purpose of the subgroup analyses is to assess the consistency of treatment effect across potential or expected prognostic factors. Additional subgroup analyses may be also be conducted.

The list of subgroups will be finalized prior to database lock but will include:

- Sex (male versus female)
- Race (white versus non-white and Asian versus non-Asian)
- Age category (< 65 years versus ≥ 65 years)
- Geographic region (United States/South America, Europe/Israel/Turkey, Asia-Pacific (excluding China/Taiwan), China/Taiwan)
- Diagnosis at randomization (candidemia only versus IC)

- Final Diagnosis (candidemia only versus IC: progression from candidemia only to IC will be determined based on the radiological and/or tissue/fluid culture assessment through Day 14)
- APACHE II score/ANC at Screening (APACHE II score ≥ 20 OR ANC < 500 cells/ μ L versus APACHE II score < 20 AND ANC ≥ 500 cells/ μ L)
- APACHE II score at Screening (≥ 20 , < 20 , 10-19, < 10)
- ANC at Screening (< 500 cells/ μ L versus ≥ 500 cells/ μ L)
- Timing of culture used to document the *Candida* infection:
 - Positive culture at randomization definition 1: Subjects with a culture from blood drawn within 12 hours prior to randomization or within 72 hours after randomization, OR a culture from another normally sterile site obtained within 48 hours prior to randomization or within 72 hours after randomization; and
 - Positive culture at randomization definition 2: Subjects with a culture from blood drawn within 12 hours prior to randomization or within 72 hours after randomization, OR a culture from another normally sterile site obtained within 96 hours prior to randomization or within 72 hours after randomization

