4.3.1. Primary Efficacy Analysis

The analysis of the **primary efficacy outcome for the FDA** will be based on the mITT population.

The non-inferiority test will be a one-sided hypothesis test performed at the 2.5% level of significance. This non-inferiority test will be based on the upper limit of the two-sided 95% confidence interval (CI). The primary efficacy outcome is the percentage of subjects that died at Day 30.

The number and percentage of subjects in each treatment group that are alive and deceased (or with missing data) at Day 30 (-2 days) will be tabulated.

The null and alternative hypotheses are as follows:

$$H_0: p_1 - p_2 \geq \Delta, \text{ and}$$

$$H_1: p_1 - p_2 < \Delta,$$

where p_1 is the all-cause mortality rate at Day 30 (-2 days) in the Rezafungin for Injection treatment group, p_2 is the primary ACM at Day 30 (-2 days) rate in the caspofungin treatment group, and Δ is the non-inferiority margin of 20%.

To test the null hypothesis, a two-sided 95% CI for the observed difference in primary outcome rates (Rezafungin for Injection treatment group minus caspofungin treatment group) will be calculated for the mITT population using the unadjusted methodology of Miettinen and Nurminen (Miettinen and Nurminen, 1985). If the upper limit of the 95% CI for the difference in the mITT population is lower than 20%, then the null hypothesis will be rejected and non-inferiority of Rezafungin for Injection versus caspofungin will be declared.

To control the overall alpha level, superiority of rezafungin for ACM at Day 30 will be tested in the following order:

- If NI is declared for ACM at Day 30 in the mITT population and the rate of ACM at Day 30 in the rezafungin treatment group is lower than the caspofungin treatment group, the

difference between the treatment groups will be tested for superiority. If the upper bound of the 95% CI is less than 0, superiority of rezafungin will be concluded.

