4.3.1.1. Additional Analyses of the Primary Efficacy Outcomes

Sensitivity analyses of the primary outcome for FDA include:

- The first sensitivity analysis will exclude subjects whose survival status is not known (these subjects are considered deaths in the primary analysis).
- The second sensitivity analysis will calculate an adjusted (for the randomization stratification factors) 95% CI interval using the stratified methodology of Miettinen and Nurminen. As noted above, Cochran Mantel Haenszel weights will be used for the stratum weights in the calculation of the CI.
- The third sensitivity analysis will be conducted using multiple imputation for missing data. Missing primary outcome data will be imputed with multiple imputation. Fifty data sets will be created by treatment group using a logistic regression in which the randomization stratification factors of diagnosis (candidemia only; invasive candidiasis)

and APACHE II score/ ANC (APACHE II score ≥ 20 OR ANC < 500 cells/ μ L; APACHE II score < 20 AND ANC ≥ 500 cells/ μ L) at Screening are included as predictive variables. The seed number of 101305 will be used. The difference in mortality rate is calculated per each imputed dataset and the risk differences are combined using proc mianalyze.

Sensitivity analyses of the primary outcome for EMA include:

- The first sensitivity analysis will consider indeterminate responses as successes.
- The second sensitivity analysis will present an unadjusted two-sided 95% CI for the observed difference in primary outcome rates (Rezafungin for Injection treatment group minus caspofungin treatment group) using the methodology of Miettinen and Nurminen.
- The third sensitivity analysis will analyze the primary outcome for the EMA in the CE population. The number and percentage of subjects with a global response of cure and failure will be provided along with an adjusted (for the randomization stratification factors) two-sided 95% CI for the difference in global cure rates.

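### The FDA primary mortality interval ignores the randomization strata; making the already planned stratified interval primary would be a small, nearly free gain, not the repair of an error

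*SAP*

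**What the plan says.** Subjects are randomized 1:1 within four cells: diagnosis (candidemia only or invasive candidiasis) crossed with APACHE II/ANC (Protocol 6.5). SAP 1.2.1 indicates a separate list per cell, since each subject receives "the next available randomization number in the respective stratum".

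- **FDA primary (mortality).** The Protocol synopsis has the interval "calculated using the unadjusted method of Miettinen and Nurminen". Protocol 13.4.1 states: "The primary analysis is based on a CI computed using the unadjusted methodology of Miettinen and Nurminen". SAP 4.3.1 says that it "will be calculated for the mITT population using the unadjusted methodology of Miettinen and Nurminen".
- **EMA primary (global cure).** Protocol 13.4.2 states: "The primary analysis is based on a CI computed using the method with stratification by Miettinen and Nurminen". The weights are Cochran-Mantel-Haenszel (CMH), and SAP 4.3.1 gives the formula.
- **Supportive analyses.** The roles are mirrored in SAP 4.3.1.1. For FDA: "The second sensitivity analysis will calculate an adjusted (for the randomization stratification factors) 95% CI interval using the stratified methodology of Miettinen and Nurminen". For EMA, the unadjusted interval is the second sensitivity analysis.
- **Superiority step (mortality).** Protocol 13.4.1.1: "If the upper bound of the 95% CI is less than 0, superiority of rezafungin will be concluded". For the whole mITT population it does not name which interval is meant. For the invasive candidiasis subgroup it names the unadjusted one.

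SAP 2.8 includes both stratification factors in a subgroup list meant "to assess the consistency of treatment effect across potential or expected prognostic factors".

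**The concern.** The trial randomizes within strata that it treats as possibly prognostic, uses those strata for one primary test and leaves them out of the other. Under stratified randomization the arms are balanced within each stratum, so differences in mortality between strata no longer contribute to the variance of the treatment difference. The unadjusted Miettinen-Nurminen variance is built from the overall rate and still includes that component. If the strata predict death, the decisive interval is somewhat too wide, and the test runs below its nominal 2.5%. At stake is a little power and precision on the FDA endpoint, and an unexplained asymmetry between the two primaries. Validity is not at stake.

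**Working it through.** **1. The plan's own figure.** Inputs from SAP 3.1: 92 per arm in mITT, 20% mortality in both arms, 20-point margin, one-sided alpha 0.025, continuity-corrected Z.

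- SE = sqrt(2 x 0.2 x 0.8/92) = 0.0590.
- Power = Phi((0.20 - 1/92)/0.0590 - 1.96) = Phi(1.247) = 89.4%, against the stated 89.7%. The statement reproduces.
- Without the correction: Phi(0.20/0.0590 - 1.96) = 92.4%. The Miettinen-Nurminen test has no continuity correction, so its power exceeds the stated value.

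**2. How much variance the strata could remove.** The documents give neither stratum shares nor stratum mortality, so these are assumptions, with overall mortality held at 20%. The ratio of stratified to unadjusted variance at equal mortality is [sum of share x p(1-p)] / [0.2 x 0.8].

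- 20% high-risk, 40% vs 15%: (0.20 x 0.24 + 0.80 x 0.1275)/0.16 = 0.1500/0.16 = 0.938
- 25% high-risk, 40% vs 13.3%: (0.25 x 0.24 + 0.75 x 0.1156)/0.16 = 0.1467/0.16 = 0.917
- 30% high-risk, 40% vs 11.4%: (0.30 x 0.24 + 0.70 x 0.1012)/0.16 = 0.1429/0.16 = 0.893
- 20% high-risk, 30% vs 17.5%: (0.20 x 0.21 + 0.80 x 0.1444)/0.16 = 0.1575/0.16 = 0.984

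**3. Effect on the error rate, large-sample check.** Take the 25%, 40/13.3 case at the margin (rezafungin 20 points worse in every stratum).

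- Within-stratum variance: 0.25(0.24 + 0.24) + 0.75(0.1156 + 0.2222) = 0.3733.
- Total variance: 0.16 + 0.24 = 0.40. Ratio 0.933.
- Unadjusted error: Phi(-1.96/sqrt(0.933)) = Phi(-2.03) = 0.021.

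**4. Simulation at the trial's size.** There were 100,000 trials per scenario: 218 randomized, blocks of 4 (assumed) in four strata, 85% evaluable, invasive candidiasis share 20.8% (the Phase 2 figure in Protocol 4.7.2), constant risk difference. Cells with fewer than 5 subjects in an arm were pooled over diagnosis within the severity stratum. Entries are unadjusted / stratified. The Monte Carlo SE of the error is about 0.0005.

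| High-risk share | ACM high/low (%) | Error at +20 | Power at 0 | Power at +5 |
|---|---|---|---|---|
| 20% | 20/20 | .0257/.0255 | .920/.920 | .686/.685 |
| 20% | 30/17.5 | .0255/.0260 | .923/.923 | .688/.690 |
| 30% | 30/15.7 | .0250/.0262 | .925/.926 | .689/.693 |
| 20% | 40/15 | .0229/.0251 | .927/.932 | .690/.704 |
| 25% | 40/13.3 | .0223/.0250 | .929/.936 | .692/.710 |
| 30% | 40/11.4 | .0215/.0255 | .931/.939 | .697/.718 |

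Mean upper limits in points (20,000 trials): 11.63/11.65 with no separation; 11.67/11.40, 11.62/11.27 and 11.56/11.11 in the three 40% cases. Superiority error at no true difference, 40% cases: .0226/.0257, .0212/.0250, .0198/.0249.

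**5. Robustness.** A separate run (184 subjects, no pooling, 200,000 trials) gave .0255/.0255 error and 92.1%/92.0% power with no separation. For 15% vs 40% it gave .0223/.0250 and 92.8%/93.2%. In a deliberately extreme case (5% vs 48%, 35% severe) it gave .0138/.0243 and 94.9%/96.1%. If effects differ across strata but average +20, the error is .0169-.0242 unadjusted and .0215-.0259 stratified. Changing the invasive candidiasis share to 30%, using blocks of 6, or letting diagnosis also predict death leaves the picture unchanged.

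**6. Sparse cells.** With 20.8% invasive candidiasis and an assumed 25% high-risk, the smallest cell averages 92 x 0.208 x 0.25 = 4.8 subjects per arm, below the threshold of 5 in SAP 4.3.1. Pooling occurred in 80%, 58% and 35% of trials in the three 40% cases. If a cell with no deaths also triggers pooling (one reading of the SAP's zero-count clause), this rises to 86%, 72% and 63%. Power stays within 0.1 point of the count-only rule.

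**The case against.** The strongest case against is that nothing is broken. The unadjusted test controls error, and mild conservatism in a mortality non-inferiority test protects against a false claim. The stratified interval is already prespecified, so both will be reported and only the label would change. At the design assumption of no difference, the gain is at most 0.8 points of power and rests on stratum rates that the documents do not give. The 1.4-2.1 point gains need 40% high-risk mortality and a drug that is truly 5 points worse. With 30% high-risk mortality, the unadjusted error is already about nominal. Sparse cells would often be pooled over diagnosis, so the four randomized strata would often not all be used. Timing is also poor. The last primary-enrollment subject was randomized on 16 August 2021, so Day 59 fell about 13 October if dosing was the same day, before SAP V4.0 of 2 November 2021. A late change that makes non-inferiority slightly easier carries a credibility cost. Finally, SAP 1.1.2 says that the agencies' expectations differ.

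Most of this stands as a limit on importance. It does not overturn the point. With no separation the cost is about 0.1 point of power. The stratified errors of .0260-.0262 in the 30% cases are close to nominal, and repeat runs gave .0252-.0253. Pooling over diagnosis keeps the severity factor, which carries the assumed gain. SAP 1.1.2 explains the separate endpoints, not the different interval methods. The timing objection is real and sets a condition on the change.

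**Conclusion.** The point holds as an efficiency improvement. The FDA primary interval does not follow the stratified randomization, the EMA primary interval does, and no reason is given. The unadjusted analysis is valid and the 89.7% power statement is sound.

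If high-risk mortality is 40% and the high-risk share 20-30%, the unadjusted one-sided error is 2.15-2.3% against 2.5-2.55% stratified. Stratifying gains 0.5-0.8 points of power at no true difference and 1.4-2.1 points at +5, and lowers the mean upper limit by 0.27-0.45 points. With 30% high-risk mortality, the gain is 0-0.1 points at no difference and 0.2-0.4 points at +5. With no separation, there is a loss of about 0.1 point. All these sizes depend on assumed stratum shares and mortality.

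**What to change.** Before database lock and while still blinded:

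1. Make the planned stratified Miettinen-Nurminen interval with CMH weights the FDA primary analysis (Protocol synopsis and 13.4.1; SAP 4.3.1), and make the unadjusted interval the sensitivity analysis in SAP 4.3.1.1.
2. State that the mITT superiority step (Protocol 13.4.1.1; SAP 4.3.1) uses the same stratified interval. The invasive candidiasis step can stay unadjusted, as it is for both endpoints.
3. Align the other FDA sensitivity analyses in SAP 4.3.1.1: stratify the one that excludes unknown survival status, and combine stratified risk differences after multiple imputation.
4. Fix a pooling rule for this interval based on subject counts and not on observed deaths. For example, if either arm of a cell has fewer than 5 subjects, pool diagnosis within the APACHE II/ANC stratum.
5. Record the change in SAP 6, which now says that there are none.

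If the FDA primary stays unadjusted, say why the two primaries differ, and apply the rule in item 4 to the stratified sensitivity analysis.

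Cost: no new subjects or data, but a protocol change and a SAP amendment (SAP 1.1.1 gives the route). It is a late change to the decisive method. The documents do not give the lock date, so the change is defensible only if it is justified and dated before unblinding.
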